### **5.4.3 Site discontinuation**

The trial site can be terminated prematurely by the sponsor if:

- The trial site deviates significantly from the protocol without prior approval from the sponsor and regulatory authorities.
- Failure of the investigator to enroll participants at an acceptable rate.
- Insufficient adherence to the protocol requirements including GCP standards and regulatory requirements.

#### **5.4.4 Trial termination**

If the investigator, the sponsor, or the sponsor's medical monitor discovers conditions arising during the trial that suggest the trial should be terminated, this can happen only after appropriate consultation between the relevant parties.

Conditions that may warrant trial termination include, but are not limited to:

- The discovery of any unexpected, significant, or unacceptable risk to the participants enrolled in ongoing trials.
- A decision on the part of the sponsor to suspend or discontinue development of AEF0117.
- Termination of the trial by the FDA, local health or regulatory authority, or IRB/EC.

Both the sponsor and the investigator reserve the right to terminate the trial, according to the terms specified in the trial contract.

The investigator must notify the IRB/EC in writing of the trial completion or early termination and send a copy of the notification to the sponsor or designee and retain one copy for the site trial regulatory file.

#### **5.4.5 Lost to follow up**

A participant will be considered lost to follow up if he or she fails to return for the scheduled visits and is unable to be contacted by the trial site staff.

The following actions must be taken if a participant fails to return to the site for a required trial visit:

- The site will attempt to contact the participant and reschedule the missed visit and counsel the participant on the importance of maintaining the assigned visit schedule and ascertain if the participant wishes to and/or should continue in the trial.
- Before a participant is deemed lost to follow up, the investigator or designee will make every effort to regain contact with the participant. These contact attempts should be documented in the participant's trial file.
- Should the participant continue to be unreachable, he or she will be considered to have withdrawn from the trial with a primary reason of lost to follow up.

#### **5.4.6 Replacement of participants**

Participants who discontinue prematurely due to safety reasons will not be replaced.

Replacements will take place if more than 4 participants administered trial drug under the same conditions (fasting or fed) drop out for other reasons than safety concern prior to Day 4 (i.e., the 72-hour PK sample).

### **5.5 Screening failures**

Persons who have signed the trial-specific informed consent and who do not meet all inclusion criteria or who meet any of the exclusion criteria at screening may be rescreened once. However,

[figure not shown]
if a person has been rescreened once and still does not meet all entry criteria, the person will remain ineligible for trial participation and will be considered screening failures. Participants who meet a dosing day exclusion criterion on Day 1 prior to randomization are also considered screening failures (see section [5.3.3](#)).

## 6 TRIAL INTERVENTION AND CONCOMITANT THERAPY

### 6.1 Trial intervention administered

AEF0117, illustrated in [Figure 1](#) below, is a chemical entity containing 7 chiral centers 3S, 8S, 9S, 10R, 13S, 14S, 17S. The stereochemical configuration at these centers is identical to those of the starting material for pregnenolone. Its molecular formula is C29H40O3 and its relative molecular mass is 436.64 g/mol.

**Figure 1 Structure of AEF0117**

AEF0117 drug substance is the 3 $\beta$ -(4-methoxybenzyloxy)pregn-5-en-20-one that is manufactured from pregnenolone. It is a very hydrophobic compound (aqueous solubility <0.1  $\mu$ g/mL and estimated log P between 5.79 and 7.15). The trial intervention and treatment arms are summarized in [Table 1](#).

**Table 1 Description of trial drug**

Intervention label	Fed group	Fasted group
Intervention name	AEF0117	AEF0117
Intervention description	One single dose in fed condition	One single dose in fasted condition
Type	Drug	
Dose formulation	Soft capsule	
Unit dose strength	1 mg	1 mg
Dosage level	1 mg as a single dose	1 mg as a single dose
Route of administration	Oral	
Use	Experimental	Experimental
Sourcing	Provided by the sponsor	
Packaging and labeling	Bottles with 21 capsules labeled according to regulatory requirements	
Description of dose and administration in each treatment arm	1 mg AEF0117 with 240 mL of water 30 minutes after start of a high fat meal	1 mg AEF0117 with 240 mL of water in fasting condition

### **6.1.1 Dosing and administration**

All participants in this trial will be dosed with a 1 mg dose of AEF0117.

The principal investigator or designee will administer the trial drug to the trial participants.

Each dose of trial drug will be administered in the morning at approximately 9 am with approximately 240 mL of room temperature water. The actual date and time of each dose administered will be recorded in the source records and the eCRF.

Each dose of the trial drug will be administered under the supervision of the clinic staff and a visual mouth check will be performed after dose administration to verify that the participant has swallowed the drug. The oral capsules must be swallowed whole and not chewed.

### **6.1.2 Packaging and labeling**

AEF0117 capsules will be supplied by Aelis Farma in dosage strengths of 1 mg. The AEF0117 trial drug is supplied in high-density polyethylene (HDPE) 30 mL bottles closed with a polypropylene (PP) cap. Each bottle contains 21 capsules.

The trial drug will be packaged and labeled in compliance with applicable federal regulations. The exact content of the actual label may be modified as long it complies with federal regulations.

The bottles with investigational products will bear at least the following information on the labels:

- Trial code
- Sponsor's name
- Name and address of manufacturer & distributor
- Trial drug description and content
- Route of administration

- Dosage form
- Packaging number
- Storage conditions
- Phrase “New drug - limited by federal law to investigational use”

Additional details will be provided in the pharmacy manual.

## **6.2 Preparation, storage, and accountability**

### **6.2.1 Preparation**

The trial drug will be supplied in bottles to the site as described above and individual participant’s single oral dose will be dispensed by a designated investigational pharmacist at the research site or other authorized personnel with appropriate training delegated by the investigator. The process will be described in the trial pharmacy manual.

### **6.2.2 Product storage and stability**

The AEF0117 formulation should be stored ambient at 20°C (68°F), with excursions permitted from 15°C to 25°C (59°F to 77°F).

The AEF0117 formulation will be monitored for stability by the sponsor’s contract manufacturing designee.

### **6.2.3 Accountability**

Responsibility for drug accountability at the trial site rests with the investigator; however, the investigator may assign some of the drug accountability duties to an appropriate pharmacist or designee. Inventory and accountability records must be maintained and must be readily available for inspection by the trial monitor and are open to inspection at any time by any applicable regulatory authorities.

The investigator or designee will retain all used, unused, and partially used containers of trial drug until the end of the trial. The investigator or designee must maintain records that document:

- Investigational product delivery to the trial site.
- The inventory at the site.
- Use by each participant.

These records should include dates, quantities, batch/serial numbers (if available), and the unique code numbers (if available) assigned to the trial drug and trial participants.

The trial drug must be used only in accordance with the protocol. The investigator will also maintain records adequately documenting that the participants were administered the trial drug as specified.

Completed accountability records will be archived by the site and in the sponsor trial master file. At the completion of the trial, the remaining trial drug will be destructed as described in the pharmacy manual.

### **6.3 Participant identification and assignment to trial intervention**

All participants will be assigned a unique trial participant number at the trial-specific screening.

A computer-generated randomization schedule will be prepared by a statistician. Eligible participants will be randomly assigned to 1 of the 2 groups. Randomization will be with a block size of 2 and stratified by sex.

The 2 groups will be divided into smaller cohorts of at least 2 participants for operational reasons (adjusted to in clinic facilities) and each cohort will include a similar number of participants from each group (fed or fasting).

### **6.4 Blinding and breaking the blind**

Not applicable since the trial is not blinded.

### **6.5 Drug exposure and compliance**

Each participant completing the trial will receive a single dose of 1 mg AEF0117.

Compliance will be recorded by the site staff administering the trial drug, see section [6.1.1](#) and [6.2.3](#).

### **6.6 Administration of meals**

Standardized breakfast, lunch, dinner, and evening snack meals at applicable times will be served to participants during the trial.

At Day 1 in the morning prior to dosing, participants will, according to randomization to fed or fasted condition, either be given a high fat breakfast in which 50% of the calories are derived from fat (FDA breakfast) (see [Appendix 4](#)) or no breakfast. The high fat breakfast should be consumed within 30 minutes, and the dose will be administered 30 minutes after the start of the meal. In case of failure to complete  $\geq 90\%$  of the meal (as assessed by visual inspection) the participant must be excluded from trial and will not be administered the trial drug. The composition of the high fat meal should be recorded in the source document.

The dose will be administered with 240 mL of water. Additional water is not allowed from 1 hour prior to dosing until 2 hours after dosing but is allowed ad libitum thereafter. Food and fluids other than water is not allowed for 4 hours post dose.

A standardized lunch will be served approximately 4 hours after dosing on Day 1 (after completion of the 4-hour assessments, see section [8.1.3.2](#)), and a standardized dinner will be served approximately 10 hours after dosing.

Noncaffeinated soft drinks and non-citrus and non-grapefruit juices will be offered with meals and ad libitum beginning 4 hours post dose. Snacks will be available and allowed from 4 hours after the dose.

The date and the exact time of administration of all meals during the confinement period should be recorded in the source documents and the eCRF.

## **6.7 Concomitant therapy**

### **6.7.1 Previous and concomitant medication**

All medications other than trial drug taken or received by the participant at any time during the trial from the first dose of trial drug through the follow-up visit or at early termination will be considered concomitant medications. All concomitant medications taken by a participant during the trial and the reason for its use must be recorded in the source documents and eCRF.

Any previous medication received within the last 30 days before dosing of the trial drug will also be recorded in the source documents and eCRF.

### **6.7.2 Restricted and/or prohibited previous and concomitant medication and foods**

The use of concomitant medications or treatments, including prescription medications, over-the-counter medications, or supplements specified as prohibited is not allowed from 2 weeks prior to receiving the trial drug until the follow-up visit. For drugs with an elimination half-life greater than 10 days, this is extended to 60 days prior to dosing of the trial drug. Occasional use of paracetamol is allowed at the discretion of the investigator.

Any use of medication during the trial should be recorded in the eCRF as concomitant medication, and use of prohibited medication should in addition be recorded as a protocol deviation. If the participant uses any prohibited medication within the first 72 hours after dosing, the investigator should discuss the participant's continued participation in the trial with the sponsor's medical monitor.

### **6.7.3 Restricted and/or prohibited therapies and foods**

Participants must refrain from foods that can affect the metabolism or absorption of some medications, including grapefruits, Seville oranges, tangelos (a cross between tangerines and grapefruit), and grapefruit juice are prohibited from 2 weeks prior to dosing and until the follow-up visit.

Participants are also requested to abstain from strenuous physical activity throughout the duration of the trial.

Consumption of alcohol and stimulating drinks (i.e., coffee, tea, chocolate, or cola like drinks) will not be allowed from 72 hours prior to admission on Day -1 until 72 hours after dosing.

Participants will be questioned about the above restrictions at each visit and the answer recorded in the source document and eCRF.

## 6.8 Rescue medication

It is anticipated that careful participant selection, dose selection and monitoring will obviate the need for emergency care. Emergency medical equipment is available in the research facility, which is in a hospital where a full medical emergency back-up team is constantly available.

In the event of an emergency, participants will be treated at the discretion of the investigator by appropriate measures.

## 7 PARAMETERS AND METHODS OF ASSESSMENT

Trial procedures and their timing are summarized in the schedule of activities in section 1.3. Protocol waivers or exemptions are not allowed.

Adherence to the trial design requirements, including those specified in the schedule of activities, is essential and required for trial conduct. However, unscheduled visits may be necessary to repeat testing following abnormal laboratory results, for follow up of AEs, or for any other reason, as needed.

All screening evaluations must be completed and reviewed to confirm that potential participants meet all eligibility criteria. The investigator will maintain a screening log to record details of all participants screened and to confirm eligibility or record reasons for screening failure, as applicable.

In the event of a significant trial-continuity issue (e.g., caused by a pandemic), alternate strategies for participant visits, assessments, and monitoring may be implemented by the sponsor or the investigator, as per local regulatory authority and IRB/EC requirements.

The maximum amount of blood collected from each participant over the duration of the trial, including any extra assessments that may be required, will not exceed 230 mL. Repeat or unscheduled samples may be taken for safety reasons or for technical issues with the samples.

### 7.1 Screening and baseline procedures

The assessments performed at screening/baseline are described in the following and their timing are summarized in the schedule of activities in section 1.3.

#### 7.1.1 Participant demography

Date of birth, sex, race, and ethnicity will be recorded for the participant demographics.

#### 7.1.2 Body measurements

Height and weight will be measured on the days noted in the schedule of activities in section 1.3. and recorded on the eCRF. Height will be measured in cm and body weight will be measured in kg with 1 decimal. BMI will be calculated as body weight in kg / (height in meters).

### 7.1.3 Medical history

Relevant previous and intercurrent diseases will be documented in the eCRF. The medical history will be obtained by interview with the participant and/or review of medical records.

## 7.2 PK parameters

### 7.2.1 Blood collection

Venous blood samples (6 mL each) to measure plasma concentrations of AEF0117 and potential metabolites will be collected at the times specified in the schedule of activities (section 1.3).

On Day -1, an indwelling catheter will be placed and may be used until the 14-hour blood sample; thereafter samples will be collected by individual venipuncture. The date and time of each blood sampling throughout the entire trial will be recorded in the eCRFs.

Detailed information regarding the procedures for PK blood sample collection, processing, storage, and shipment are described in [Appendix 3](#).

### 7.2.2 Bioanalytical methodology

The plasma samples will be analyzed for AEF0117 by a validated assay method. The bioanalytical method for the metabolites will be developed.

The samples will be analyzed by: Biotrials Bioanalytical Services, Laval, Quebec, Canada.

### 7.2.3 PK analysis

For each evaluable participant, the PK parameters will be calculated from the plasma concentrations of AEF0117 using non-compartmental methods. The PK parameters are listed in [Table 2](#). Additional details are described in section [9.6](#).

**Table 2 Plasma PK parameters**

PK parameter	Definition
$C_{\max}$	maximum observed plasma concentration
$C_{\min,24h}$	minimum observed (or trough) plasma concentration within 24 hours after dosing
$C_{\text{last}}$	last measurable plasma concentration
$T_{\max}$	time to maximum plasma concentration
$T_{1/2}$	terminal elimination half-life
$T_{\text{lag}}$	the delay in achieving $T_{\max}$
$T_{\text{last}}$	time to last measurable plasma concentration
$AUC_{0-24}$	area under the plasma concentration-time curve from time zero (pre-dose) to 24 hours
$AUC_{0-t}$	area under the plasma concentration versus time curve from time 0 (pre-dose) to the last quantifiable concentration time point, calculated using the linear trapezoid rule
$AUC_{0-\infty}$	area under the plasma concentration versus time curve from time 0 (pre-dose) to infinity, calculated using the linear trapezoid rule
CL/F	apparent oral clearance, calculated as dose/ $AUC_{0-\infty}$
% $AUC_{\text{extrap}}$	percentage of $AUC_{0-\infty}$ due to extrapolation from $T_{\text{last}}$ to infinity $([AUC_{0-\infty} - AUC_{0-t}] / [AUC_{0-\infty}]) \times 100$
Vd/F	apparent volume of distribution

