### 3 TRIAL OBJECTIVES AND ENDPOINTS

Objectives	Endpoints
Primary objective	Primary endpoints
To determine the bioavailability of orally administered AEF0117 after fed conditions relative to fasting conditions in healthy volunteers.	Bioavailability of AEF0117 after fed conditions relative to fasting conditions. PK parameters $C_{max}$ , $T_{max}$ , $T_{lag}$ , $AUC_{0-t}$ , $AUC_{0-\infty}$ determined based on plasma concentration in serial blood sample collections up to 312 hours after dosing.
Secondary objectives	Secondary endpoints
To evaluate other PK parameters of AEF0117 in healthy volunteers.	PK parameters $\%AUC_{extrap}$ , $C_{min,24h}$ , $t_{1/2}$ , CL/F, and Vd/F determined based on plasma concentration in serial blood sample collections up to 312 hours after dosing.
To evaluate safety and tolerability of a single dose of 1 mg AEF0117 in healthy volunteers.	Vital signs (BP, HR) and ECG. AEs.
Exploratory objective	Exploratory endpoints
To characterize potential metabolites regarding plasma PK.	Identification of metabolites, to the extent feasible, and PK of potential metabolites of AEF0117 in plasma. To the extent concentration in plasma allows, the following PK parameters will be estimated: $C_{max}$ , $T_{max}$ , $AUC_{0-t}$ , $AUC_{0-\infty}$ , and $C_{min,24h}$ , and $C_{last}$ .

 Exploratory endpoints will be reported separately.

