### 4 TRIAL DESIGN

#### 4.1 Overview

This is a single center, randomized, parallel-group, 2-arm, open-label, single-dose trial in healthy male and female volunteers aged 18–55 years to obtain data on the effect of food on the oral bioavailability of AEF0117.

A total of 32 healthy volunteers are planned to be enrolled. Participants will be randomized in a 1:1 ratio to receive 1 dose of AEF0117 1 mg in fasted condition (16 participants) or fed condition (16 participants). The participants will be divided into smaller cohorts of minimum 2 participants for operational reasons (adjusted to capacity of the research facility) and each cohort will include 1 fasting participant and 1 participant receiving breakfast prior to dosing.

The total trial duration for an individual participant will be up to 6 weeks (42 days) from screening (up to 28 days prior to dosing) to the final follow-up visit (14 days after dosing).

After screening, the trial includes 2 days where the participants are confined at the research facility, and thereafter 7 visits to the site (6 visits and a follow-up visit). Participants will stay in the research facility from the afternoon prior to dosing on Day 1 and until after collection of the blood sample 24 hours after dosing (i.e., Day 2) and then be discharged.

Participants will be admitted to the research facility during the afternoon on Day -1 where it will be verified that the participants are still eligible according to the inclusion and exclusion criteria,

and the baseline assessments will be performed. After an overnight stay in the research facility, participants will be randomized to fasted or fed state and dosed with a single oral dose of 1 mg AEF0117.

Blood samples for determination of AEF0117 and potential metabolites of AEF0117 in plasma will be collected before dosing and repeatedly for up to 2 weeks after dosing.

Safety will be monitored throughout the trial by assessment of AEs, suicidal risk, clinical safety laboratory parameters, pregnancy tests (females only), vital signs, ECGs, and physical examinations.

The schedule of activities summarizing all procedures is provided in section 1.3, and a description of procedures by visit is provided in section 8.1.

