### 4.2.2 Justification for dose and route

AEF0117 is formulated as a soft capsule for oral administration. In this parallel-group food-effect bioavailability trial, a single dose will be administered to each participant.

The 1 mg dose has been selected since it is considered the highest therapeutic dose and has been shown to reduce the abuse-related subjective effects of cannabis and its self-administration in a phase 2a trial. Once daily administration of 1 mg dose for 5 days in patients with CUD has shown good safety and tolerability. In healthy volunteers, multiple dosing of up to 6 mg once daily for 7 days was considered safe and well tolerated with no SAEs, and only 2 moderate and no severe TEAEs.

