15. Use of any prescription or over-the-counter drug therapy, including psychoactive and/or psychotropic medication, herbal, homeopathic, vitamins, minerals, and nutritional supplements, bodybuilding supplements unapproved by the sponsor, within 2 weeks prior to receiving the trial drug (for drugs with an elimination half-life greater than 10 days, this will be extended to 60 days).
16. Use of a drug therapy, or diet or supplements (e.g., St. John's Wort) food and fruit juices (e.g., grapefruit juice) known to induce or inhibit hepatic drug metabolism within 30 days prior to receiving trial drug or during the trial.
17. Legal status that would interfere with participation.
18. Unable to follow the restrictions outlined in the protocol.

---

 Screening laboratory samples must be collected between Day -28 and -2 and evaluated at the latest on Day -1. Eligibility for randomization is based on the screening results unless abnormal results from the baseline samples collected at Day -1 are available prior to randomization on Day 1.

19. Ingestion of an investigational drug or product, or participation in a drug trial within a period of 90 days prior to receiving trial drug.

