#### **8.1.3.2 Post dose assessments**

- Resting 12-lead ECG will be obtained in a supine position at 1, 2, 4, 8, and 11 hours post dose and prior to blood sampling.
- Resting BP and HR will be measured in a supine position at 1, 2, 4, 8, and 11 hours post dose and prior to blood sampling.
- Blood samples (6 mL each) for determination of plasma AEF0117 concentration will be collected at 1, 1.5, 2, 3, 4, 5, 6, 8, 11, and 14 hours post dose.
- Blood samples (6 mL each) for determination of plasma concentration of potential metabolites will be collected at 2, 4, 6, 8 and 11 hours post dose.
- Recording of any concomitant medications.
- AE assessment throughout the day by querying with non-leading questions and observation.
- Water is allowed ad libitum from 2 hours after dosing. Snacks and noncaffeinated soft drinks and non-citrus and non-grapefruit juices will be offered with meals and ad libitum beginning at lunch.

- Lunch will be consumed by participants approximately 4 hours after dosing of trial drug, after completion of the 4-hour assessments.
- Dinner will be consumed by participants approximately 10 hours after dosing of trial drug.
- An evening snack will be offered to the participants at approximately 21.30 pm.

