#### **8.1.4 Day 2 (confinement period)**

The following evaluations and procedures will be performed on Day 2:

- A brief physical examination will be performed.
- Pre-breakfast body weight will be measured.
- Resting 12-lead ECG will be obtained in a supine position at 24 hours post dose and prior to any blood sampling.
- Resting BP, HR, and oral temperature will be measured in a supine position at 24 hours post dose and prior to any blood sampling.
- AE assessment by querying with non-leading questions and observation.
- Recording of any concomitant medications.
- Collection of blood samples for:
  - Fasting (6 hours) safety laboratory parameters (chemistry, hematology, and coagulation profile) at 24 hours post dose.
  - Determination of plasma AEF0117 concentration (6 mL) at 24 hours post dose.
  - Determination of plasma concentration of potential metabolites (6 mL) at 24 hours post dose.
- Collection of urine for urinalysis.
- C-SSRS evaluation will be performed (Since Last Visit version).
- Breakfast will be consumed.

When all the above procedures have been performed, participants will be discharged from the research facility.

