## 9.6.2 Secondary endpoints

Additional PK parameters of AEF0117, including  $C_{min,24h}$ ,  $t_{1/2}$ , %AUCextrap, CL/F, and Vd/F will be calculated using non-compartmental methods and summarized by graphic displays and descriptive statistics as data permit. Individual and summary (means  $\pm$  SD for each condition i.e., fed/fasting) plasma AEF0117 concentration-time plots will be displayed graphically.

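### Cmin,24h is defined as a minimum or a trough, which are different quantities after a single dose: the lowest value can be the 1-hour absorption sample, not the 24-hour concentration

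*Protocol*

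**What the plan says.** Table 2 (section 7.2.3) and the list of abbreviations define Cmin,24h as the "minimum observed (or trough) plasma concentration within 24 hours after dosing". The synopsis and section 3 make it a secondary endpoint for AEF0117 and an exploratory endpoint for metabolites. Section 9.6.2 says the secondary parameters "will be calculated using non-compartmental methods and summarized by graphic displays and descriptive statistics as data permit".

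The design is a "single center, randomized, parallel-group, 2-arm, open-label, single-dose trial" (section 4.1), and section 4.2.2 repeats that "a single dose will be administered to each participant". Section 5.3.2 excludes anyone with "Ingestion of an investigational drug or product, or participation in a drug trial within a period of 90 days prior to receiving trial drug".

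On Day 1, AEF0117 samples "will be collected at 1, 1.5, 2, 3, 4, 5, 6, 8, 11, and 14 hours post dose" (section 8.1.3.2). The Day 2 list in section 8.1.4 adds "Determination of plasma AEF0117 concentration (6 mL) at 24 hours post dose". For metabolites, the synopsis and section 8.1.3.2 place the first post-dose sample at 2 hours, and section 8.1.4 schedules one at 24 hours. Section 4.2.1 calls the elimination half-life long but gives no value.

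The protocol nowhere limits the minimum to times after Tmax or fixes it at 24 hours.

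**The concern.** Over a dosing interval at steady state, the minimum and the trough are normally the same number, so the definition's *or* does no harm. After one dose from a baseline of about zero, the curve rises and then falls, and the sampled minimum lies at one end of the post-dose window. That is either the first sample, which reflects how quickly absorption has begun and may be below quantification, or the 24-hour sample, which is the trough of interest for a once-daily drug. A long half-life keeps the 24-hour value high and so favours the first sample.

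A meal may change the onset of absorption, and the protocol lists Tlag and Tmax under its primary endpoint, so a delay is something it means to measure. Under one label, the endpoint could then describe onset in both arms, or onset in fed participants and 24-hour exposure in fasted ones. At stake is one reported secondary parameter: a fed group with higher 24-hour concentrations could be summarised with a lower Cmin,24h.

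**Working it through.** **The plan's own figure.** The only design calculation is the power in section 9.1: CV 0.3, true ratio 1.25, upper limit 1.75, two-sided 90% CI. On the log scale, SD = sqrt(ln(1 + 0.3²)) = 0.2936 and the distance to the limit is ln(1.75/1.25) = 0.3365. The noncentrality is 0.3365 / (0.2936 × sqrt(2/n)), which is 3.03 for n = 14 and 2.81 for n = 12 per group. The noncentral t distribution gives 90.4% and 85.9%, matching the stated 90% and 86%. Cmin,24h plays no part in it.

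**Inputs for the minimum.** From the protocol: post-dose samples at 1, 1.5, 2, 3, 4, 5, 6, 8, 11, 14 and 24 hours, and a fed/fasted exposure ratio of 1.25. Assumed, because the protocol gives no values: absorption rate ka, lag, half-life, and no AEF0117 left from any earlier exposure.

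**Model A: one compartment, first-order absorption, lag L.** C(t) = F × ka/(ka − k) × [exp(−k(t − L)) − exp(−ka(t − L))], and zero before L, with F = 1 fasted and 1.25 fed. With a half-life of 48 h, k = ln 2/48 = 0.01444 per hour.

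- Fasted, ka 0.5, L 0.25: C(1) = 1.0297 × (0.9892 − 0.6873) = 0.311 and C(24) = 1.0297 × 0.7097 = 0.731. The minimum is at 1 h.
- Fed, ka 0.3, L 0.5: C(1) = 1.3132 × (0.9928 − 0.8607) = 0.174 and C(24) = 0.934. The minimum is at 1 h.
- Ratio of minima: 0.1735/0.3109 = 0.56. Ratio at 24 h: 0.934/0.731 = 1.28.

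The same formula with other fed-arm values, keeping the fasted arm and the 48 h half-life:

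| Fed ka (/h), lag (h) | Ratio of minima | Ratio at 24 h |
|---|---|---|
| 0.5, 0.25 (extent only) | 1.25 | 1.25 |
| 0.4, 0.25 | 1.04 | 1.26 |
| 0.4, 0.5 | 0.73 | 1.26 |
| 0.3, 0.5 | 0.56 | 1.28 |
| 0.3, 0.75 | 0.29 | 1.28 |
| 0.3, 1.0 | 0 | 1.29 |

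In every row both arms have their minimum at 1 h. With a half-life of 12 h, fasted ka 1.0 with lag 0.25 and fed ka 0.4 with lag 0.75, the arms separate. The fasted minimum is 0.269 at 24 h and the fed minimum is 0.118 at 1 h, a ratio of 0.44 against 1.42 at 24 h.

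**Model B: fast then slow decline.** Disposition rates are 0.25 and ln 2/100 per hour, with weights 0.9 and 0.1. Fasted ka is 0.8 with no lag, and fed ka is 0.5. Each exponential takes the Model A form, and the two are summed with their weights. The fasted minimum is 0.0887, at 24 h.

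| Fed lag (h) | Fed minimum, time | Ratio of minima | Ratio at 24 h |
|---|---|---|---|
| 0 to 0.8 | 0.113 to 0.115, 24 h | 1.27 to 1.29 | 1.27 to 1.29 |
| 0.85 | 0.0888, 1 h | 1.00 | 1.30 |
| 0.9 | 0.0603, 1 h | 0.68 | 1.30 |
| 0.95 | 0.0307, 1 h | 0.35 | 1.30 |
| 1.0 | 0, 1 h | 0 | 1.30 |

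**With variability between participants.** Model A was simulated with 14 per arm, 400 trials per scenario, half-lives of 12 to 150 h and a fed lag of 0.75 h. About 24% of fed participants had a 1-hour value of zero. The median ratio of arm means was 0.24 to 0.44 for the minimum and 1.25 to 1.44 at 24 h. When food changed only the extent of absorption, the ratio of minima stayed near 1.25.

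**The case against.** The strongest reply is that little hangs on this parameter. Section 9.6.1 plans a fed/fasted ratio and 90% CI only for Cmax, AUC0-t and AUC0-∞. The 24-hour sample is taken, section 9.3 has all data listed, and section 9.6.2 plans concentration-time plots by condition, so a misleading Cmin,24h would show against the profile. All of that stands and limits the weight of the point.

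A second reply is that the word trough and the 24h subscript already point to the 24-hour value. They permit that reading, but the definition also names the minimum and does not choose. Nor is this a detail left to the SAP: the protocol states the rule, so an SAP following it inherits the ambiguity.

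A third reply is that the reversal depends on assumed kinetics. That also stands. In Model B nothing goes wrong until the fed lag exceeds about 0.85 h, and the two models disagree on which sample is the fasted minimum.

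A reader might also infer more than the documents support:

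- *The pre-dose sample makes Cmin,24h zero for everyone.* The definition says after dosing, and that sample precedes the dose. A zero can arise only from an early post-dose sample.
- *A zero would ruin a planned geometric mean.* Section 9.3 includes geometric means only as applicable, and section 9.6.2 names none for this parameter. Handling of values below quantification is ordinary SAP content.
- *The 24-hour concentration is lost.* It is collected, listed and plotted.
- *Minimum and trough never agree after one dose.* In Model B's fasted arm they do.

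**Conclusion.** The definition is unsuited to a single-dose design. It joins two quantities that need not agree, and taken as the minimum it can return the 1-hour absorption sample, differently by arm. If food delays absorption enough, the group summaries of Cmin,24h can run opposite to 24-hour exposure: a ratio of minima of about 0.35 to 0.7 for moderate delays, lower or zero for longer ones, against about 1.25 to 1.3 at 24 hours. These sizes rest on assumed absorption rates, lags and half-lives, on the protocol's 1.25 exposure ratio, and on a pre-dose level of about zero. If food changes only the extent of absorption, the direction is kept, although a minimum at 1 hour still does not describe a trough.

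It would be tempting to say that the trial's fed/fasted comparison reverses. The documents do not support that: no formal comparison of this parameter is planned, and the primary analysis and power are untouched. This is a correction worth making to one descriptive secondary endpoint and its exploratory metabolite counterpart.

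**What to change.** Replace Cmin,24h with C24h, defined as *observed plasma concentration at 24 hours after dosing*, in Table 2, the list of abbreviations, the synopsis (section 1.1), and sections 3, 9.6 and 9.6.2. Make the same change to the exploratory metabolite endpoint in the synopsis and section 3. The parameter then has one meaning in both arms and serves as the once-daily trough time point.

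The cost is wording only. The 24-hour samples for AEF0117 and for metabolites are already scheduled, so no extra sample, assay or visit is needed.
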